8.1. Efficacy Endpoints and Analyses

8.1.1. Clinical Outcomes

For subjects treated with cefiderocol alone, the number and proportion of subjects in each category will be calculated for each time point (EOT and Posttreatment visit and at EOS). Subjects will be presented by cohort and overall, for the ITT and MITT Populations. Note that the study is not designed to collect outcome data at EOS on all subjects, and summaries for Clinical Outcomes will be underestimated due to indeterminate caused by missing data.

For subjects treated with cefiderocol alone, the number and proportion of subjects in each category and each baseline Gram-negative pathogen will be calculated for each time point (EOT, and Posttreatment visit and at EOS). Subjects will be presented by cohort and overall, for the MITT Population.

In addition, the proportion of clinical cure rate at Post treatment visit by each baseline pathogen and MIC will be calculated.

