4.5 Withdrawal of Subjects from the Study or Discontinuation from Study Treatment

Withdrawal or discontinuation is defined as subjects who provide assent and/or whose parent(s)/LAR(s) provide consent to participate in the study but, the subject or parent/LAR wish to stop their participation in the study, or in the investigator's opinion, the safety of the subject is at risk.

The investigator will make every reasonable attempt to complete the study for each study subject. A subject may withdraw assent to participate in the study or a subject's parent(s)/LAR may withdraw consent for the subject's participation in the study at any time, for any reason.

The investigator or subinvestigator may discontinue a subject from study treatment at any time for any of the following reasons:

- A serious or intolerable AE occurs and the investigator or subinvestigator considers that the subject should discontinue study treatment
- Progression of the study-qualifying infection (poor or no response, aggravation, or relapse of current infection) for which the investigator considers that the subject should discontinue study treatment
- The subject recovers from the infection and antibiotic treatment is no longer required
- The subject is proven to be ineligible for the study after dosing/entry into the study
- The investigator or subinvestigator determines that the subject should be discontinued from the study treatment based on the management and discontinuation criteria for abnormal liver function tests ([Appendix 2](#))
- The study is prematurely terminated
- The investigator or subinvestigator determines that the subject should be discontinued from study treatment for any other reasons

In the event a subject withdraws assent, and/or a subject's parent(s)/LAR withdraws consent, the subject will be discontinued from the study and no further assessments will be done. However, in the event a subject is prematurely discontinued from study treatment by the investigator or subinvestigator but assent and consent from the study have not been withdrawn, EOT (or early termination) procedures including physical examination, vital sign measurements, and clinical laboratory tests will be performed and the reporting of AEs will be obtained until the EOS visit (28 [+ 7] days after administration of the last dose of study treatment).

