7.6.1.1.1 HAP/VAP/cIAI

- **Clinical Cure:** Resolution or substantial improvement of baseline signs and symptoms of pneumonia/cIAI.
- **Clinical Failure:** No apparent response to therapy; persistence or worsening of baseline signs and/or symptoms of pneumonia/cIAI; reappearance of signs and/or symptoms of pneumonia/cIAI; development of new signs and/or symptoms of pneumonia/cIAI requiring antibiotic therapy other than, or in addition to, study treatment therapy; progression of chest radiographic abnormalities; or death due to pneumonia/cIAI.
- **Indeterminate:** Lost to follow-up such that a determination of clinical cure/failure cannot be made.

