7.6.1.1.2 Complicated Urinary Tract Infection

- **Clinical Cure:** Resolution or substantial improvement of baseline signs and symptoms of cUTI, or return to preinfection baseline if known, such that no antibiotic therapy is required for the treatment of the current infection.
- **Clinical Failure:** No apparent response to therapy; persistence or worsening of baseline signs and/or symptoms of cUTI; or reappearance of signs and/or symptoms of cUTI; development of new signs and/or symptoms of cUTI requiring antibiotic therapy other than, or in addition to, study treatment therapy; or death due to cUTI.
- **Indeterminate:** Lost to follow-up such that a determination of clinical cure/failure cannot be made.

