7.5.2. Concomitant Therapy

Concomitant therapy (Concomitant antibiotic therapy, Concomitant Standard of Care Treatment for Disease, Concomitant Non-Antibiotic therapy) is defined as any therapy administered after study drug is administered in the study.

This document is confidential.

8. Efficacy

Efficacy endpoints will be evaluated for subjects in the multiple-dose phase of the study for the ITT and MITT analysis Populations.

The efficacy endpoints are as follows:

- Clinical outcome, defined as the categories below:

HAP/VAP/cIAI:

- Clinical Cure: Resolution or substantial improvement of baseline signs and symptoms of pneumonia/cIAI.
- Clinical Failure: No apparent response to therapy; persistence or worsening of baseline signs and/or symptoms of pneumonia/cIAI; reappearance of signs and/or symptoms of pneumonia/cIAI; development of new signs and/or symptoms of pneumonia/cIAI requiring antibiotic therapy other than, or in addition to, study drug therapy; progression of chest radiographic abnormalities; or death due to pneumonia/cIAI.
- Indeterminate: Lost to follow-up such that a determination of clinical cure/failure cannot be made.

cUTI:

- Clinical Cure: Resolution or substantial improvement of baseline signs and symptoms of cUTI, or return to pre-infection baseline if known, such that no antibiotic therapy is required for the treatment of the current infection.
- Clinical Failure: No apparent response to therapy; persistence or worsening of baseline signs and/or symptoms of cUTI; or reappearance of signs and/or symptoms of cUTI; development of new signs and/or symptoms of cUTI requiring antibiotic therapy other than, or in addition to, study drug therapy; or death due to cUTI.
- Indeterminate: Lost to follow-up such that a determination of clinical cure/failure cannot be made.

BSI/Sepsis:

- Clinical Cure: Resolution or substantial improvement of baseline signs and symptoms. Subjects with bacteremia must have eradication of bacteremia caused by the Gram-negative pathogen.
- Clinical Failure: No apparent response to therapy; persistence or worsening of baseline signs and/or symptoms, reappearance of signs and/or symptoms; development of new signs and/or symptoms requiring antibiotic therapy other than, or in addition to, study drug therapy; or death due to BSI/sepsis.
- Indeterminate: Lost to follow-up such that a determination of clinical cure/failure cannot be made.

This document is confidential.

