- Microbiological outcome per pathogen defined as the categories below:

HAP/VAP/cIAI and BSI/Sepsis:

- Persistence: Continued presence of the baseline Gram-negative pathogen from an appropriate clinical specimen.
- Indeterminate: No culture obtained from an appropriate clinical specimen or additional antibiotic therapy for the treatment of the current infection including missed sampling for reasons other than a successful clinical outcome.
- Eradication: Absence of the baseline Gram-negative pathogen from an appropriate clinical specimen. If it is not possible to obtain an appropriate clinical culture and the subject has a successful clinical outcome, the response will be presumed to be eradication.

cUTI:

- Persistence: A urine culture shows that the baseline Gram-negative uropathogen found at entry at $\geq 10^5$ CFU/mL grows to $\geq 10^3$ CFU/mL.
- Indeterminate: No urine culture obtained or additional antibiotic therapy for the treatment of the current infection including missed sampling.
- Eradication: A urine culture shows that the baseline Gram-negative uropathogen found at entry at $\geq 10^5$ colony forming units (CFU)/mL is reduced to $< 10^3$ CFU/mL.

Clinical response will be characterized based on an evaluation of clinical signs and symptoms by the investigator or designee. Clinical outcomes will be characterized at EOT, Posttreatment, and EOS if available.

The microbiological outcomes per subject determined by investigator will be entered in the eCRF. When the investigator confirms:

- that the subject experiences eradication of all baseline Gram negative pathogens then “Eradication” will be entered. For subjects with baseline infection other than cUTI who achieved clinical cure at corresponding visit, the response will be considered as Eradicated.
- that the subject experiences persistence of any baseline Gram-negative pathogen then “Persistence” will be entered
- that the subject experiences anything other than above then “Indeterminate” will be entered.

Emergent (ie, nonbaseline) pathogens will be considered separately, and will not affect the per-subject microbiological outcome.

This document is confidential.

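### Clinical outcome is scored visit by visit with no rule for an earlier failure or a rescue antibiotic, so a failed and rescued child can be counted as a clinical cure

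*SAP*

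**What the plan says.** - **Scoring and tabulation.** SAP Section 8 states: "Clinical outcomes will be characterized at EOT, Posttreatment, and EOS if available". For children on cefiderocol alone, SAP 8.1.1 adds that "the number and proportion of subjects in each category will be calculated for each time point (EOT and Posttreatment visit and at EOS"). SAP 8.2.1 applies the same tabulation to children on cefiderocol plus SOC and to all treated children.
- **Cure, HAP/VAP/cIAI** (Protocol 7.6.1.1.1): "Resolution or substantial improvement of baseline signs and symptoms of pneumonia/cIAI".
- **Cure, BSI/sepsis** (SAP Section 8): improvement in signs and symptoms, plus "Subjects with bacteremia must have eradication of bacteremia caused by the Gram-negative pathogen".
- **Cure, cUTI** (Protocol 7.6.1.1.2): improvement or return to the preinfection state, "such that no antibiotic therapy is required for the treatment of the current infection".
- **Failure.** All three definitions include no response, persistence, worsening or reappearance. They also include new signs or symptoms "requiring antibiotic therapy other than, or in addition to, study treatment therapy" in the protocol, or "requiring antibiotic therapy other than, or in addition to, study drug therapy" in the SAP.
- **Nonresponse.** SAP 6.4.2 treats only lost, missing or indeterminate outcomes as nonresponse.
- **Stopping for failure.** Protocol 4.5 lists, among the reasons to stop study treatment, "Progression of the study-qualifying infection (poor or no response, aggravation, or relapse of current infection").
- **Microbiological outcome.** SAP Section 8 lists additional antibiotic therapy for the current infection under Indeterminate. It also says that, outside cUTI, a child with clinical cure at a visit is taken as eradicated at that visit.

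**The concern.** The plan foresees children who stop cefiderocol because the infection progresses, and Protocol 5.1.2 lets the investigator change SOC at any time. It does not say how such a child is scored afterwards. Outside cUTI, the cure definitions do not ask what produced the recovery, so a recovery due to another drug can be credited to cefiderocol.

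The secondary objective is read at the Posttreatment and EOS visits (Protocol Section 2, SAP 3.2), which come after any rescue. The cure and eradication summaries by baseline pathogen and MIC (SAP 8.1.1 and 8.1.2, Tables 14.2.1.3 and 14.2.1.6) use the Posttreatment visit alone, so no EOT row stands beside them to show an earlier failure. The AE tables need not show it either: under Protocol 7.5.4.1, progression of the qualifying infection up to the Posttreatment visit is not an AE unless its outcome is serious. The caveats in SAP 8.1.1 and 8.1.2 mention only underestimation, so a reader would not look for an error in the other direction.

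**Working it through.** **1. Can the rescued child be a cure?** Take a child who fails on cefiderocol, is given another antibiotic and is well at the Posttreatment visit, 7 ± 4 days after EOT, that is day 3 to day 11.

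| Infection | Antibiotic condition in the cure definition | Can the child be Clinical Cure? |
|---|---|---|
| HAP/VAP/cIAI | None | Yes |
| BSI/sepsis | None; bacteremia must be eradicated | Yes, once any bacteremia has cleared |
| cUTI | No antibiotic still required | Only after the rescue course is no longer needed |

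The same child can also fit the failure wording if failure is read as covering the whole period since baseline. Neither document says whether failure is judged at the visit or cumulatively, and none ranks the two categories. The defect is therefore two overlapping categories with no precedence, so two sites could score the same child differently.

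**2. Does it spread to the microbiological outcome?** Outside cUTI, yes. The rescued child fits Indeterminate (additional antibiotic therapy) and also fits the override that turns clinical cure into eradication. SAP Section 8 does not say which prevails.

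**3. Which tables?** The all-subjects tables are affected wherever the child is classified. The pathogen-by-MIC tables are affected too, on the reading that they cover all MITT children, since their titles carry no restriction to cefiderocol alone. The cefiderocol-alone table is affected only if a rescued child stays in that group. The protocol glossary defines an SOC antibiotic as any antibiotic given for the qualifying infection, and a rescue drug fits that definition. No rule says whether the child then moves to the combination group.

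**4. Size.** The plan's minimum numbers reproduce: 4 × 6 + 3 × 10 = 24 + 30 = 54. Outcome applies only to the multiple-dose phase, with 10 per cohort and 30 overall.

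- Shift per affected child: 1/10 = 10.0 points in a cohort; 1/30 = 3.3 points overall.
- Let f be the share failing on cefiderocol and r the share of those who are rescued, well and scored as cure at Posttreatment. The reported cure rate is (1 − f) + f × r, against 1 − f with failure carried forward. Both f and r are assumptions; the documents give neither.

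| f | r | Failure carried forward | Scored by visit | Shift |
|---|---|---|---|---|
| 10% | 50% | 90% | 95% | 5 |
| 20% | 80% | 80% | 96% | 16 |
| 30% | 100% | 70% | 100% | 30 (ceiling) |

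- Chance of at least one affected child, 1 − (1 − f × r)^n. For f = 10%, r = 50%: 40.1% with n = 10 and 78.5% with n = 30. For f = 20%, r = 80%: 82.5% and 99.5%.

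These figures assume that every other child is scored Clinical Cure, with no indeterminate outcomes. The size of the cefiderocol-alone group is not stated, so no figure can be given for it; a smaller group gives a larger shift per child.

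**The case against.** A reader might infer that every rescued child becomes a cure, that the bias always favours cefiderocol, and that the secondary cefiderocol-alone result is inflated. The documents do not support that.

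- Outcome is an investigator judgement (Protocol 7.6.1), and an investigator may reasonably record failure for a child who needed another drug.
- After treatment is stopped, Protocol 4.5 names EOT procedures and AE reporting but no Posttreatment outcome. If none is recorded, SAP 6.4.2 counts the child as a nonresponder. Against this, footnote m to the multiple-dose schedule in Protocol Appendix 1 sets an outcome assessment at Posttreatment and exempts no one.
- A rescued monotherapy child may be moved out of the cefiderocol-alone group, which would keep that cure out of the secondary table.
- For cUTI, the antibiotic condition blocks cure during rescue, and additional antibiotic therapy already makes the microbiological outcome Indeterminate.
- Efficacy is descriptive, there is no hypothesis testing (SAP 6.1), and Protocol 7.7 presents the efficacy assessments as supplemental and deliberately loose. A failure recorded at EOT remains visible in the EOT row.

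All of this stands, and it limits the certainty and importance of the point. It does not close the gap. The rules still permit the cure score outside cUTI, and the Posttreatment-only summaries have no EOT row. In combination children the EOT row may itself come after rescue, because SOC belongs to study treatment and EOT follows its last dose.

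**Conclusion.** The point holds as a gap in the scoring rules. A failed and rescued child with HAP/VAP/cIAI, or with BSI/sepsis after any bacteremia clears, can be scored Clinical Cure at Posttreatment or EOS and then Eradicated. For cUTI, cure is possible only once no antibiotic is required, and the override does not apply.

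The upward error is possible rather than certain. It amounts to 10 points per affected child in a cohort of 10 and 3.3 points in 30. The illustrations of 90% reported as 95% and 80% reported as 96% rest on assumed failure and recovery rates. A reported 100% would need every failed child to recover and be scored as cured. Any effect on the cefiderocol-alone result depends on a classification that the plan leaves undefined. The primary safety and PK objectives are untouched.

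**What to change.** Add to SAP 6.4.2 and Section 8, as rules for analysis only:

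1. A subject scored Clinical Failure at a visit, or given a new antibiotic for the qualifying infection because of failure, is counted as Clinical Failure at all later visits, in both the ITT and MITT tables.
2. The rule that turns clinical cure into eradication does not apply to these subjects. Their microbiological outcome stays Persistence or Indeterminate as already defined.
3. Cefiderocol alone versus cefiderocol plus SOC is classified by the regimen before rescue.
4. The failure definitions are reconciled: the protocol refers to study treatment, which includes SOC, and the SAP to study drug, which does not.

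The cost is a small derivation on data already collected, with no new visits or assessments. Reported cure rates may be slightly lower.

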8.1.2. Microbiological Outcomes

For subjects treated with cefiderocol alone, the number and proportion of subjects in each category will be calculated for each time point (EOT, and Posttreatment visit and at EOS). Subjects will be presented by cohort and overall, for the MITT Populations. Note that the study is not designed to collect outcome data at EOS on all subjects, and summaries for microbiological outcomes will be underestimated due to indeterminate caused by missing data

For subjects treated with cefiderocol alone, the number and proportion of each category by each baseline Gram-negative pathogen will be calculated for each time point (EOT and Posttreatment visit and at EOS if available). Subjects will be presented by cohort and overall, for the MITT Population.

In addition, the proportion of eradication rate at Post treatment visit by each baseline pathogen and MIC will be calculated.

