6.4.2. Missing Microbiological or Clinical Outcome

For clinical and microbiological outcomes, subjects who are lost to follow-up or have missing or “indeterminate” outcomes will be included in the denominator as indeterminate for cure/eradication rate, ie, considered as nonresponders.

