8.2. Exploratory Efficacy Endpoints and Analyses

8.2.1. Clinical Outcomes

For subjects treated with cefiderocol in combination with SOC, the number and proportion of subjects in each category will be calculated for each time point (EOT, Posttreatment and EOS). Subjects will be presented by cohort and overall, for the ITT and MITT Populations. The same analysis will be performed for subjects with cefiderocol + SOC and all subjects treated with cefiderocol.

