Table 14.1.3.2.3 Baseline Characteristics (MITT Population)
Table 14.1.3.2.4.1 Baseline Gram-negative Pathogen (MITT Population)
Table 14.1.3.2.4.2 Baseline Gram-negative Pathogen for Subjects Treated With Cefiderocol Alone or Combination With SOC (MITT Population)
Table 14.1.3.2.5 Summary of Minimum Inhibitory Concentration of Baseline Gram-negative Pathogens with Interpretation of Susceptibility Determined by Clinical and Laboratory Standards Institute (MITT Population)
Table 14.1.3.2.6 Summary of Minimum Inhibitory Concentration of Baseline Gram-negative Pathogens with Interpretation of Susceptibility Determined by European Committee on Antimicrobial Susceptibility Testing (MITT Population)
Table 14.1.3.3.1 Summary of Medical History by System Organ Class and Preferred Term (Safety Population)
Table 14.1.3.3.2 Summary of Medical History by System Organ Class and Preferred Term (MITT Population)
Table 14.1.5 Summary of Extent of Exposure and Compliance to Study Drug (Safety Population)
Table 14.1.4.1.1 Summary of Prior Antibiotic Medications (Safety Population)
Table 14.1.4.1.2 Summary of Prior Non-Antibiotic Medications (Safety Population)
Table 14.1.4.1.3 Summary of Prior Standard of Care Treatment for Disease (Safety Population)
Table 14.1.4.2.1 Summary of Concomitant Antibiotic Medications (Safety Population)
Table 14.1.4.2.2 Summary of Concomitant Non-Antibiotic Medications (Safety Population)
Table 14.1.4.2.3 Summary of Concomitant Standard of Care Treatment for Disease (Safety Population)
Table 14.2.1.1.1 Summary for Clinical Outcome Per Subject By Time Point (ITT Population)
Table 14.2.1.1.2 Summary for Clinical Outcome By Time Point for Subjects Treated With Cefiderocol Alone or Combination With SOC (ITT Population)
Table 14.2.1.1.3 Summary for Clinical Outcome By Time Point for Subjects Treated With Cefiderocol Alone or Combination With SOC (MITT Population)
Table 14.2.1.2 Summary of Clinical Outcome per Baseline Gram-negative Pathogen By Time Point (MITT Population)
Table 14.2.1.3 Summary of Clinical Outcome at Post Treatment per Baseline Pathogen and Minimum Inhibitory Concentration Values Determined by Clinical and Laboratory Standards Institute (MITT Population)
Table 14.2.1.4.1 Summary for Microbiological Outcome Per Subject By Time Point (MITT Population)
Table 14.2.1.4.2 Summary for Microbiological Outcome By Time Point for Subjects Treated With Cefiderocol Alone or Combination With SOC (MITT Population)

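### The pooled eradication rate mixes two missing-culture rules, so it moves with the cUTI share and culture availability as well as with the drug effect

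*SAP*

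**What the plan says.** **Outside cUTI.** For HAP/VAP/cIAI and BSI/sepsis, SAP Section 8 (Efficacy) provides that, where no suitable culture can be obtained and "the subject has a successful clinical outcome, the response will be presumed to be eradication". Protocol Section 7.6.2.1.1 has the same rule.

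**cUTI.** The SAP's Indeterminate category reads "No urine culture obtained or additional antibiotic therapy for the treatment of the current infection including missed sampling". Neither SAP Section 8 nor Protocol Section 7.6.2.1.2 makes an exception for clinical cure.

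**Per-subject outcome.** SAP Section 8 adds: "For subjects with baseline infection other than cUTI who achieved clinical cure at corresponding visit, the response will be considered as Eradicated". The sentence does not require the culture to be missing.

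**Rate.** Under SAP Section 6.4.2, missing and indeterminate outcomes "will be included in the denominator as indeterminate for cure/eradication rate, ie, considered as nonresponders".

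**Presentation.** For cefiderocol alone, SAP Section 8.1.2 says "Subjects will be presented by cohort and overall, for the MITT Populations", and adds breakdowns by baseline pathogen and by pathogen with MIC. Section 8.2.2 uses cohort and overall for combination therapy and for all treated subjects. Infection type appears only as a baseline summary, in SAP Section 7.2.

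**Culture schedule.** The Protocol Synopsis (Microbiological Outcome) and Section 3.1 leave specimen timing to routine care. Section 7.5.3.2 asks for specimens after treatment starts only where possible and clinically indicated.

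**A second protocol rule.** The Synopsis, Section 3.1 and Appendix 1 (multiple-dose note n) permit presumed eradication on clinical cure when no post-treatment culture can be had, and they do not except cUTI.

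**The concern.** Take two children who are both clinically cured and both without a follow-up culture. One had pneumonia and counts as an eradication. The other had cUTI and counts as a nonresponder. Only the infection type separates them.

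Missing cultures are likely under this design. Specimens are taken when clinically indicated, recovered children are plausibly the least likely to be cultured, and the EOS visit may be a phone call.

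Microbiological response with cefiderocol alone is part of the secondary objective. If both groups share one denominator, a low pooled rate may reflect a high cUTI share with few urine cultures. A high rate may rest largely on presumption. Age cohorts shown side by side could differ simply because their infection mix differs.

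**Working it through.** **The plan's own figures.** The only size figure is the enrolment minimum: 4 × 6 + 3 × 10 = 54, of which 30 are in the multiple-dose phase. This agrees with Protocol Section 3.1. The documents give no expected eradication rate, cure rate, culture rate or cUTI share, so all four are assumptions below.

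**Per-pathogen rule.** Let q be the share with a follow-up culture, e the eradication rate on culture, c the clinical cure rate among those without a culture, and s the cUTI share. Take q, e and c as equal in the two infection groups.

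- Non-cUTI rate: q·e + (1 − q)·c
- cUTI rate: q·e
- Pooled rate: q·e + (1 − s)(1 − q)·c

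Pooled rate (%) with e = c = 80%:

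| q | s = 0% | 20% | 50% | 80% | 100% |
|---|---|---|---|---|---|
| 0.3 | 80.0 | 68.8 | 52.0 | 35.2 | 24.0 |
| 0.5 | 80.0 | 72.0 | 60.0 | 48.0 | 40.0 |
| 0.9 | 80.0 | 78.4 | 76.0 | 73.6 | 72.0 |
| 1.0 | 80.0 | 80.0 | 80.0 | 80.0 | 80.0 |

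Example at q = 0.5: 0.5 × 0.8 + 0.8 × 0.5 × 0.8 = 0.72 at s = 20%, and 0.5 × 0.8 + 0.2 × 0.5 × 0.8 = 0.48 at s = 80%. With 30 evaluable subjects that is 21.6 against 14.4 expected eradications.

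**Case mix against drug effect.** Raising e = c from 60% to 90% at s = 50% moves the pooled rate by 0.30 × (0.5 + 0.5q). Moving s from 20% to 80% at e = c = 80% moves it by 0.48 × (1 − q).

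| q | Drug effect 60% to 90% (points) | cUTI share 20% to 80% (points) |
|---|---|---|
| 0.3 | 19.5 | 33.6 |
| 0.5 | 22.5 | 24.0 |
| 0.9 | 28.5 | 4.8 |

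The two are equal where 0.48(1 − q) = 0.15(1 + q), so q = 0.33/0.63 ≈ 0.52.

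**One common rule.** If a missing culture were Indeterminate for everyone, the rate would be 80% × q (40% at q = 0.5, 72% at q = 0.9). If cure without a culture were eradication for everyone, it would be 80% at every q. Under either rule the cUTI share drops out.

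**Per-subject sentence read literally.** If clinical cure alone makes a non-cUTI subject eradicated, and culture and clinical results are taken as independent, then with every subject cultured the non-cUTI rate is 1 − 0.2 × 0.2 = 96%, against 80% in cUTI. On that reading, complete culturing does not remove the gap.

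**The case against.** The strongest defence is purpose. Protocol Section 7.7 treats efficacy as supplemental and deliberately not rigorous, SAP Section 6.1 excludes inferential testing, and the sample size ignores efficacy. No between-cohort comparison is planned. All of that stands, and it limits how serious the point is.

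The tables also give every category, so a reader would see many Indeterminates rather than many Persistences, and SAP Section 8.1.2 warns of underestimation. This helps only in part. The warning concerns EOS and one direction of error. It does not mention eradication presumed without a culture, and the Eradication category does not distinguish presumed from documented. By-pathogen tables do not solve the problem either, since one species can cause both cUTI and other infections.

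Table titles do not list every grouping: SAP Section 7.2 plans baseline pathogens by infection site, yet the title of Table 14.1.3.2.4.1 does not say so. The shells are not in the supplied text. A split could therefore exist there, but Sections 8.1.2 and 8.2.2 do not state one.

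A reader might infer four stronger things, none of which the documents support:

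- **That the rate reflects the cUTI share rather than the drug.** It reflects both. On the assumed values, case mix outweighs a 60%-to-90% drug difference only when fewer than about 52% are cultured.
- **That the two rules are opposite.** They diverge only for clinically cured subjects without a culture. Without cure, a missing culture is Indeterminate in both groups.
- **That the pooled rate could run from 100% to 0% on case mix alone.** This needs every subject cured and none cultured, and nothing in the documents says no cultures will be taken.
- **That clinical outcome needs the same split.** Clinical outcome carries no presumption from a missing culture, so the request does not follow from this defect.

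**Conclusion.** The concern holds as a reporting defect in a secondary, descriptive endpoint. The missing-culture rule differs by infection type, Indeterminate is "considered as nonresponders", and the planned text pools the groups. The pooled eradication rate therefore depends on cUTI share and culture availability as well as on the drug.

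For a shift in cUTI share from 20% to 80%, the size is 24 points if half are cultured and 4.8 points if 90% are. Under the per-pathogen rule it is zero if all are cultured. These figures assume 80% eradication and 80% cure, equal in both groups. The direction does not depend on those values: whenever some cured subjects lack a culture, a larger cUTI share lowers the pooled rate.

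It would go too far to say that the endpoint cannot be interpreted. The category counts remain informative, and SAP Section 6.1 puts all subject data in listings. What the planned tables do not show is how much eradication was documented and how much nonresponse is simply an absent urine culture.

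Two textual problems add to this. The protocol gives two different rules for cured cUTI subjects without a culture. The SAP's per-subject sentence can also collide with its own Persistence category when a cured non-cUTI subject has a positive culture. That sentence is not in Protocol Section 7.6.2.1, although SAP Section 12 reports no changes from the protocol.

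**What to change.** 1. In the overall multiple-dose microbiological tables (14.2.1.4.1, 14.2.1.4.2 and 14.2.1.5), present cUTI and non-cUTI separately.
2. Split Eradication into documented (negative culture) and presumed (clinical cure, no culture).
3. Keep the pooled figure only with a footnote saying that it mixes two missing-culture rules.
4. Reconcile the Protocol Synopsis, Section 3.1 and Appendix 1 note n with Protocol Section 7.6.2.1.2 and SAP Section 8 on presumed eradication in cUTI.
5. State whether a positive culture overrides the SAP's per-subject clinical-cure sentence. If the sentence stays, record it in SAP Section 12.

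No new data collection appears to be needed: infection type is already summarized at baseline, and the outcome and culture data are already captured. The cost is one grouping and one extra category, with small cells. At the minimum of 10 per cohort, an even split leaves 5 per group, before restriction to MITT and to cefiderocol alone. The split should therefore be made overall rather than within each cohort.
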